## 3. INTERIM ANALYSIS AND DATA MONITORING COMMITTEE REVIEW

No interim analysis and data monitoring committee review is planned for this study.

#### 4. SUBJECT INFORMATION

Unless specified otherwise, FAS will be used for the subject information analyses and participants will be analyzed according to the treatment group to which they were randomized at Week 0, regardless of the treatment they actually received. The number of participants in FAS will be summarized by treatment group and overall.

Simple descriptive statistics, such as mean, median, standard deviation, interquartile range, maximum, and minimum for continuous variables, and counts and percentages for discrete variables will be used to summarize most data and no formal hypothesis testing for treatment comparisons will be performed. In addition, participant listings will also be used to present the data.

#### 4.1. Demographics and Baseline Characteristics

The FAS will be used for all tabulations. Participants' demographic data and baseline disease characteristics will be summarized by treatment group. If imbalances are found at baseline, then additional analyses may be performed adjusting for baseline differences.

#### 4.1.1. Demographic

Table 1 presents a list of the demographic variables that will be summarized by treatment group, and overall for the FAS.

Continuous Variables:	Summary Type	
Age (years)	Descriptive statistics (N. mean.	
Weight (kg)	standard deviation [SD], median and range [minimum and	
Height (cm)	maximum], and IQ range).	
Categorical Variables:		
Age (<40 years, 40 to <65 years, and $\geq$ 65 years)		
Sex (male, female)	Frequency distribution with the	
Weight (kg) ( $\leq 95$ kg, $> 95$ kg)	number and percentage of	
Race (American Indian or Alaska Native, Asian, Black or African American, White, Other)	participants in each category.	
Ethnicity (Hispanic or Latino, Not Hispanic or Latino)		
BMI (Normal [<25], Overweight [25 -<30], Obese [≥30])		

Table 1:Demographic Variables

## 4.1.2. Baseline Disease Characteristics

Baseline disease severity measurements (e.g., duration of HS disease, baseline Hurley stage status, baseline AN count, inflammatory nodule count, abscess count, and draining and non-draining fistula count, HS-PGA, Modified Hidradenitis Suppurativa Score) and baseline patient reported outcomes (e.g, DLQI, HSSD, NRS Pain, NRS Itch, EQ-5D-3L, HADS) will be summarized by treatment group.

## 4.1.3. Medical History

Summaries of participants' surgical history, alcohol intake, and smoking status will be provided by treatment group. Medical history will be listed including body systems and condition/non-drug allergy as captured on the eCRF.

## 4.2. Disposition Information

The number of participants in the following disposition categories will be summarized by treatment group and overall:

- Participants screened: met the inclusion criteria regarding the target indication and signed the informed consent
- Participants randomized
- Participants randomized and received at least 1 study agent
- Participants who completed the study through Week 16 and Week 36
- Participants who discontinued study and the reasons for discontinuation through Week 16 and Week 36

Listings of participants will be provided for the following categories:

• Participants who discontinued study Participants who were unblinded during the study period

## 4.3. Treatment Compliance

Study agent compliance will be summarized descriptively through Week 16 and through the end of study (Week 36) for the FAS. Number of the participants receiving each scheduled treatment will be summarized. In addition, treatment compliance will also be assessed by protocol deviations related to study agent administration (i.e., incorrect study agent or dose received).

## 4.4. Extent of Exposure

The exposure data through Week 16 and through Week 36 will be summarized. The number and percentage of participants who receive study agent will be summarized by treatment group for the safety analysis set. Descriptive statistics will be presented for the following parameters:

- Number of administrations
- Cumulative total dose

In addition, the average exposure (number of administrations) and average duration of follow-up (weeks) will also be summarized by treatment group in the safety tables through different study time periods.

## 4.5. **Protocol Deviations**

In general, the following list of major protocol deviations may have the potential to impact participants' rights, safety or well-being, or the integrity and/or result of the clinical trial. Participants with major protocol deviations will be identified prior to database lock and will be summarized by category by treatment group through Week 36 for the FAS.

- Entered study and did not satisfy entry criteria
- Received wrong treatment or incorrect dose
- Received excluded concomitant or non-drug therapy
- Out of window visit
- Out of window procedure
- Other

A listing of participants with major protocol deviations and a listing of patients who missed scheduled study agent administration will also be provided by randomized treatment group. In addition, analyses of COVID-19 related protocol deviations will be provided.

## 4.6. Prior and Concomitant Medications/Surgeries

Prior and concomitant medications will be summarized by treatment group for the FAS. Prior medications are defined as any therapy used before the day of first dose (partial or complete) of study agent. Concomitant medications are defined as any therapy used on or after the same day as the first dose of study agent, including those that started before and continue on after the first dose of study agent.

Prior biologic used that was captured in eCRF, summary of concomitant medications with potential to improve HS and summary of concomitant analgesic therapy will be summarized by randomized treatment group for the FAS. a listing of participants who received a concomitant treatment that could improve HS, a listing of participants who received concomitant analgesic therapy, and a listing of participants who received concomitant corticosteroids will be provided.

## 5. EFFICACY

## 5.1. General Method of Analysis

Unless specified otherwise, efficacy data summaries will be provided by treatment group for the FAS. Statistical comparisons will be made between each of the bermekimab treatment groups (400 mg SC qw, 400 mg SC q2w) and the placebo treatment group.

In general, for response efficacy endpoints, treatment comparisons will be performed using a Cochran-Mantel-Haenszel (CMH) test stratified by the prior biologic use (yes/no) and screening Hurley stage (II/III). For continuous efficacy endpoints, treatment comparisons will be performed using either a Mixed-Effect Model Repeated Measure (MMRM) model. All of the models will have treatment group, prior biologic use (yes/no), screening Hurley stage (II/III), and baseline value for the corresponding efficacy endpoint as explanatory factors. The MMRM model will also include visit, treatment group by visit interaction, prior biologic use by visit, screening Hurley stage by visit, and baseline value by visit interaction as additional explanatory factors. In addition, treatment differences and their associated 95% confidence intervals will be presented.

For the MMRM model, an unstructured covariance matrix for repeated measure within a participant will be used. In case that convergence cannot be achieved, autoregressive (1) covariance structure will be used.

Descriptive statistics, such as mean, median, standard deviation, minimum and maximum, interquartile range for continuous variables, and counts and percentages for categorical variables will be used to summarize the data. Graphical data displays and subject listings may also be used to summarize the data.

# 5.2. Analysis Specifications

## 5.2.1. Level of Significance

Unless otherwise specified, all statistical testing procedures will be performed at a 2-sided significance level of 0.05. Multiplicity adjustment was planned for the primary endpoint as specified in protocol Section 10.5.3 to maintain an overall Type I error of 0.05 or less for the primary endpoint analysis. Nominal p-values will be reported for other secondary analyses.

However, since this is a Phase 2 trial and stricter multiplicity adjustment for the primary endpoint at an overall alpha level of 0.05 is not required; a less stringent type I error controlled will be implemented instead. The study would be considered as positive if any of the comparisons for primary endpoint analysis (weekly injection group vs placebo, and every other week injection group vs placebo) is less than or equal to 0.05. Therefore, an overall Type I error rate will be maintained at 0.1 or less for the primary endpoint analysis. Nominal p-values will be reported for secondary analyses.

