10.1 DETERMINATION OF SAMPLE SIZE

The primary efficacy endpoint is percent of patients who have a positive HiSCR score (achiever) at week 12. The positive HiSCR score is defined as $a \ge 50\%$ reduction in inflammatory lesion AN count (sum of abscesses and inflammatory nodules), and no increase in abscesses or draining fistulas in HS compared with the lesions counted at baseline. The sample size is calculated for the bermekimab weekly injection group (Treatment Arm 1) versus placebo group (Treatment Arm 3) comparison (the primary comparison).

Assuming a positive HiSCR score is achieved in 60% of intent-to-treat (ITT) patients treated in the bermekimab weekly injection group (Treatment Arm 1) versus 30% in placebo treated patients (Treatment Arm 3), then, for a randomization ratio of 1:1:1, a sample size of 126 patients (42 in each treatment group) is required for approximately 80% power at a 0.05 significance level using a 2-sided Pearson chi-square test. In order to account for possible dropouts and to provide adequate safety data, approximately 150 patients will be randomized and treated.

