10.5.3.1 Primary Efficacy Analysis

For the primary efficacy endpoint, the two bermekimab treatment groups will be compared with placebo. To account for these two comparisons, testing will be done in a sequential manner, each at the 0.05 alpha level. The bermekimab weekly injection group (Treatment Arm 1) will be compared to the placebo group (Treatment Arm 3) first. If this test is significant at the 0.05 level, then the bermekimab every other week injection group (Treatment Arm 2) will be compared to the placebo group (Treatment Arm 3). Otherwise, the P-value for Treatment Arm 2 vs Treatment Arm 3 will be considered nominal. This method to control the type-1 error will only be implemented for the primary efficacy analysis variable.

The number and percentage of patients who have a positive HiSCR score (achiever) at week 12 will be presented by treatment group. Patients who terminate from the study early prior to week 12 will count as non-responders (non-achievers) in the primary efficacy analysis (Non-Responder Imputation). If a patient received rescue medication, the patient will be counted as a non-responder from the start of rescue medication. Additional treatment failure rules and sensitivity analyses will be discussed in the statistical analysis plan.

A Cochran-Mantel-Haenszel (CMH) general association test stratified by prior anti-tumor necrosis factor or IL-17 inhibitor therapy use (yes/no) and Hurley Stage (II/III) will be used to compare each bermekimab dose separately with placebo. The primary efficacy analysis population will be the mITT population.

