## 5.3.4. Analysis Methods

The primary endpoint will be compared between the each bermekimab group and the placebo group. The primary endpoint will be analyzed at Week 12 based on the composite strategy (Section 5.3.2) and the data from all participants in FAS (Section 2.4.1.1) will be analyzed according to randomized treatment group regardless of the treatment actually received.

In this primary analysis, the number and proportion of participants who achieve a HiSCR at Week 16 will be summarized for each treatment group. To address the primary objective, a CMH chi-square statistic stratified by stratified by prior biologic use (yes/no) and screening Hurley stage (II/III) at an alpha level of 0.05 will be used.

The proportion of participants who achieve HiSCR at Week 12 will be compared between each of the 2 bermekimab treatment groups and the placebo group. The proportion difference between each bermekimab group and placebo group and its 2-sided 95% CI will be provided based on normal approximation with Mantel-Haenszel weights adjusting for prior biologic use (yes/no) and screening Hurley stage (II/III).

The study would be claimed as positive if any of the comparisons for primary endpoint analysis (weekly injection group vs placebo, and every other week injection group vs placebo) is less than or equal to 0.05. Therefore, an overall Type I error rate will be maintained at 0.1 or less for the primary endpoint analysis.

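### Does the SAP's rule that either dose can make the study positive, in place of the protocol's fixed sequence, need to be changed?

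*SAP*

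**What the plan says.** **Protocol.** Section 10.5.3.1 compares both bermekimab groups with placebo on HiSCR at Week 12. On multiplicity it says: "To account for these two comparisons, testing will be done in a sequential manner, each at the 0.05 alpha level". Arm 1 is tested first, and Arm 2 follows if Arm 1 is significant. "Otherwise, the P-value for Treatment Arm 2 vs Treatment Arm 3 will be considered nominal". Section 10.1 sizes the trial on Arm 1 versus placebo and, in a parenthesis, calls that contrast the primary one.

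**SAP.** Section 5.2.1 first recalls the protocol: "Multiplicity adjustment was planned for the primary endpoint as specified in protocol Section 10.5.3", with the aim of keeping the overall error at 0.05. It then says that strict control at that level is not needed in a Phase 2 trial and that "a less stringent type I error controlled will be implemented instead". The new rule begins "The study would be considered as positive if any of the comparisons for primary endpoint analysis" and is met when either p-value is at most 0.05. Its stated consequence is that "an overall Type I error rate will be maintained at 0.1 or less for the primary endpoint analysis". Section 5.3.4 repeats the rule where the primary analysis is specified: "The study would be claimed as positive if any of the comparisons for primary endpoint analysis" meets the same threshold. Section 1.3 states a superiority hypothesis for bermekimab that names no lead dose. Section 1.4 keeps the Arm 1 sample size but does not call that comparison primary.

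**The concern.** The two documents give different success rules for the primary endpoint. They part in one pattern only: Arm 2 has p ≤ 0.05 and Arm 1 does not. A reader of the SAP would then call the study positive. A reader of the protocol would say that the comparison it calls primary was missed and that the Arm 2 p-value is nominal.

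At stake is the headline conclusion, and an overall false-positive rate that rises from 5% towards 10%. Timing adds to the unease. HiSCR is in the Week 16 lock (SAP 2.4) and identified sponsor staff are unblinded at that lock (SAP 1.5.2), so a label left unsettled could look as if it had been chosen after the data were seen. The supplied SAP carries no date, so nothing can be inferred about when the rule was changed.

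**Working it through.** **Inputs.** Two-sided 0.05 per comparison (SAP 5.2.1); 1:1:1 allocation, 60% versus 30%, 42 per arm, about 150 randomised, so about 50 per arm (Protocol 10.1, SAP 1.4). The documents give no Arm 2 response rate. Every rate below other than 60% for Arm 1 and 30% for placebo is an assumption.

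**1. The plan's own figures.**

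- Error bound: 0.05 + 0.05 = 0.10, as the SAP states.
- Sample size, Pearson chi-square with pooled variance: n = [1.96·√(2·0.45·0.55) + 0.8416·√(0.6·0.4 + 0.3·0.7)]² / 0.3² = (1.3790 + 0.5646)² / 0.09 = 41.97, so 42 per arm and 126 in total. Power by the same formula is 80.0% at 42 per arm and 86.6% at 50. Both rules test Arm 1 at 0.05, so these figures hold under either.

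**2. Attained error with no effect in either arm.** The two test statistics share the placebo arm. With equal allocation each difference has variance 2σ²/n and their covariance is σ²/n, so the correlation is 0.5.

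- Two-sided, either arm: 1 − P(|Z1| < 1.96, |Z2| < 1.96) = 1 − 0.9093 = 0.0907. Independent tests would give 1 − 0.95² = 0.0975. Both lie inside 0.10.
- Two-sided, Arm 2 only: 0.0907 − 0.05 = 0.0407.
- In favour of bermekimab, either arm: 1 − P(Z1 < 1.96, Z2 < 1.96) = 1 − 0.9546 = 0.0454.
- In favour of bermekimab, Arm 2 only: 0.0454 − 0.025 = 0.0204.

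The hypothesis in SAP 1.3 is superiority, so the favourable figures are the ones that bear on a false claim of benefit. Under the fixed sequence the two-sided overall error is 0.05.

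**3. How often the labels differ.** Exact enumeration of three binomials with the unstratified chi-square test, without continuity correction. The planned test is a stratified CMH, so the figures are approximate for it. Placebo is 30% throughout.

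| Arm 1 / Arm 2 rate | Arm 2 only, 50 per arm | Arm 2 only, 42 per arm |
|---|---|---|
| 30% / 30% (no effect, two-sided) | 4.0% | 4.1% |
| 60% / 60% | 8.1% | 10.4% |
| 50% / 50% | 17.1% | 17.4% |
| 45% / 45% | 15.6% | 15.2% |
| 60% / 50% | 2.9% | 3.8% |
| 60% / 45% | 1.2% | 1.7% |
| 30% / 60% | 83.8% | 79.2% |

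The last row needs the weekly arm to equal placebo while the less frequent regimen reaches 60%. Nothing in the documents suggests that; it is a bound only.

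**4. What the SAP rule buys.** At 60%/60%/30% and 50 per arm, the enumerated chance of a positive study is 87.6% if Arm 1 must succeed and 95.8% if either arm may: a gain of about 8 points.

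**5. An example.** Placebo 15/50, Arm 1 24/50, Arm 2 25/50.

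- Arm 1: z = 0.18/√(0.39·0.61·2/50) = 1.845, p = 0.065.
- Arm 2: z = 0.20/√(0.40·0.60·2/50) = 2.041, p = 0.041.

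The SAP calls this study positive and the protocol calls the Arm 2 p-value nominal. The counts, differences, intervals and p-values are the same either way.

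**The case for a change.** The strongest case for a change is about authority. For the primary analysis, Protocol 10.5.3.1 leaves to the SAP only further treatment-failure rules and sensitivity analyses. Protocol 10 foresees SAP revisions for amendments or unexpected problems in execution or data, and the SAP's reason (Phase 2) is neither. Protocol 11.3 requires an approved amendment to modify the protocol, and none that touches this rule is supplied. If the two regimens work about equally, 8% to 17% of trials at 50 per arm fall in the disputed pattern, which is not remote.

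That much stands: the documents differ, and the protocol text was not brought into line. It does not show that the analysis will mislead. Each document says what an Arm 2-only result is called, so no rule is missing, and the SAP tells its reader that it departs from the protocol and what error rate results.

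The possible remedies gain little:

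- Amending the protocol to the SAP's rule changes no result and carries the full approval process of Protocol 11.3.
- Restoring the sequence in the SAP reverses a deliberate choice: an Arm 2-only result could no longer be called positive.
- Requiring the report to say that the Arm 1 comparison was missed would, under the SAP's rule, bring the double label back, because the word primary would still stand in Protocol 10.1.

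**Conclusion.** The mismatch is real, but no change to the plan follows. The SAP openly exchanges a 5% overall error for at most 10% so that either dose can carry the study, and it states the price correctly: about 9.1% attained two-sided, about 4.5% in favour of bermekimab. That is a fair trade-off in a Phase 2 trial meant to explore dose effects, and it fits a hypothesis that names no lead dose.

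The effect is confined to one label in one pattern of results. In favour of bermekimab that pattern arises in about 2% of trials with no effect. At 50 per arm it arises in about 1% to 8% if Arm 1 reaches the planned 60%, and about 1% to 17% across active rates of 45% to 60%. These ranges assume 30% on placebo, an Arm 2 rate no higher than that of Arm 1, and an unstratified test; a better Arm 2 would raise them.

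If the sponsor amends the protocol for another reason, aligning sections 10.5.3.1 and 10.1 with the SAP would be sensible housekeeping. It would belong before any unblinded efficacy review, because the protocol also permits unblinded interim analyses and, in its wording, the Week 16 lock is optional. The conclusion does not depend on it.

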# 5.2.2. Data Handling Rules

No imputation will be performed for missing baseline values.

For the main analysis of primary endpoint of HiSCR at Week 12, participants who discontinued treatment will be considered as a non-responder from that point onward. The remaining missing data will be imputed as non-responder. Supplementary analyses will be performed and include (1) using observed data regardless of whether the participant discontinued treatment or have missing data, and (2) data after treatment discontinuation will be considered as missing, missing response will be imputed by multiple imputation methods under the assumption of missing at random. Similar data handling rules (i.e., main analysis with non-responder imputation and

2 supplementary analyses) will also be applied for HiSCR response over time through Week 16. The following data handling rules will be applied for other endpoints:

Binary secondary endpoints:

• Analyses will be similar to the main analysis of the primary endpoint. A participant who discontinued treatment will be considered as a non-responder from that point onward. The remaining missing data will be imputed as non-responder.

Continuous secondary endpoints:

- If a participant discontinued treatment, zero will be assigned to improvement or percent improvement. Remaining missing data will not be imputed. A MMRM model will adjust for missing post baseline data and all available data from the 3 treatment groups through Week 16 or from Week 16 through Week 36 will be included. Under the assumption of missing at random (MAR), the missing data will be accounted for through correlation of repeated measures in the model.
- In addition, supplementary analyses will be performed for the analyses related to (a) change from baseline in AN count (Section 5.4.3.2.2) and (b) change from baseline in HSSD past 24 hours pain (Section 5.4.3.5.3.2) endpoints using
  - Observed data regardless of whether the subject discontinued treatment or have missing data.
    - Data after treatment discontinuation will be considered as missing, missing data will be addressed by MMRM model.

## 5.2.3. Treatment Groups

In the efficacy analyses, full analysis set will be used and the participants will be analyzed according to the randomized treatment groups they were assigned to, regardless of the treatments they actually received. Unless otherwise specified, efficacy analyses during each of study periods below are in general displayed as follows:

- Analysis through Week 16
  - Efficacy analyses for placebo comparison at Week 16 or through Week 16 will be summarized by randomized treatment group at Week 0:
    - Placebo: Participants randomized to placebo group at Week 0.
    - **Bermekimab 400 mg q2w**: Participants randomized to bermekimab 400 mg SC q2w group at Week 0.
    - **Bermekimab 400 mg qw**: Participants randomized to bermekimab 400 mg qw group at Week 0.
    - **Combined Column**: Combined column which combines the data from the randomized and treated participants who are assigned to bermekimab treatment groups at baseline.

- Analysis from Week 16 through Week 36
  - Efficacy data from Week 16 through Week 36 will be summarized by the following treatment groups:
    - **Placebo**  $\rightarrow$  **Bermekimab** 400 mg qw: efficacy in participants randomized to placebo group at week 0 who crossed over to receive Bermekimab 400 mg qw at Week 16.
      - Only placebo participants crossover to bermekimab 400 mg SC qw and received bermekimab at Week 16 will be included in the summary for the visits after Week 16.
    - **Bermekimab 400 mg q2w**: Participants randomized to bermekimab 400 mg SC q2w group at Week 0.
    - **Bermekimab400 mg qw**: Participants randomized to bermekimab 400 mg SC qw group at Week 0.
    - **Combined Column**: Combined column which combines the data from the randomized and treated participants who are assigned to bermekimab treatment groups at baseline.

These presentations allow assessment of efficacy over time between treatment groups.

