## 2.4.1. Efficacy Analysis Set(s)

## 2.4.1.1. Full Analysis Set

The full analysis set (FAS) includes all randomized participants who received at least 1 dose of study agent. This analysis set will be used for the efficacy analyses of the endpoints through Week 36, *unless otherwise specified*.

In the efficacy analyses, participants will be analyzed according to the randomized treatment groups they were assigned to, regardless of the treatments they actually received.

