## 5.4.1. Analysis Methods

The secondary efficacy analyses outlined in the following sections in general will be carried out at key endpoints (Week 12 and Week 16) and over time.

Most of the secondary efficacy analyses described in sections below will be based on FAS. For participants randomized to placebo, only participants who crossed over to receive bermekimab at Week 16 will be included in the efficacy summaries for the visits after Week 16. All statistical testing will be performed at the 2-sided 0.05 significance level. Nominal p-values will be presented.

## 5.4.1.1. At Week 12 and Week 16

For continuous endpoints where longitudinal data were collected prior to the analysis visits; treatment comparisons will be performed using Mixed-Effect Model Repeated Measure (MMRM) model, with fixed effects for treatment, week, stratification factors (prior biologic use (yes/no), screening Hurley stage (II/III)) when sample size in each category of the stratification variables is permitted, and baseline value in the model. The MMRM model will also include prior biologic use by visit, screening Hurley stage by visit, and baseline value by visit interaction and the treatment-by-week interaction as additional explanatory factors.

The model will be performed based on all available data from the 3 treatment groups through Week 16. The treatment difference between a guselkumab group and the placebo group will be estimated by the difference in the least squares means (LSmeans). The 95% CIs for the differences in LSmeans and p-values will be calculated.

For binary response endpoints treatment comparisons will be performed using a Cochran-Mantel-Haenszel (CMH) test stratified by the prior biologic use (yes/no) and screening Hurley stage (II/III) with missing data imputed with Non-Responder Imputation (NRI) defined in Section 5.2.2.

For the PRO endpoints with ordinal scale, the Cochran-Mantel-Haenszel (CMH) mean scores test stratified by prior biologic use (yes/no) and screening Hurley stage (II/III) will be used to compare bermekimab and placebo. The distribution of ordinal scale category will also be provided.

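### After Week 16 the placebo-crossover column drops early discontinuers while the qw, q2w and combined columns count them as failures, so crossover versus continuous dosing is not like for like

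*SAP*

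**What the plan says.** SAP 5.2.3 defines the efficacy columns for Week 16 through Week 36. For the placebo-to-qw column it says "Only placebo participants crossover to bermekimab 400 mg SC qw and received bermekimab at Week 16 will be included in the summary", applied to visits after Week 16. SAP 5.4.1 repeats the restriction for the placebo arm: "only participants who crossed over to receive bermekimab at Week 16 will be included in the efficacy summaries for the visits after Week 16".

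The other columns in the same list are defined at randomization: "Participants randomized to bermekimab 400 mg SC qw group at Week 0" and "Participants randomized to bermekimab 400 mg SC q2w group at Week 0". The combined column pools these two groups as randomized and treated. None requires dosing at Week 16. The default population is the full analysis set (all randomized with at least one dose), of which SAP 2.4.1.1 says "This analysis set will be used for the efficacy analyses of the endpoints through Week 36".

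For binary endpoints SAP 5.2.2 says "A participant who discontinued treatment will be considered as a non-responder from that point onward". For continuous endpoints it assigns zero improvement after discontinuation. SAP 5.4.2 treats missing binary responses over time as non-response.

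SAP 5.2.3 closes the list of displays with "These presentations allow assessment of efficacy over time between treatment groups".

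**The concern.** A qw or q2w patient who stops at Week 6 is counted as a failure at every efficacy visit after Week 16 (Weeks 20, 24, 28, 32 and 36). A placebo patient who stops at Week 6 is missing from the crossover column at those same visits. Early discontinuation therefore lowers the displayed response in the continuous-dosing columns and not in the crossover column, even when the drug works equally well in both.

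HiSCR at Week 32 is a secondary endpoint in Protocol 3.1 and falls inside this display. Someone reading across the columns could take the denominator difference for a treatment difference, and the SAP's closing sentence invites that reading.

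**Working it through.** **Inputs**
- Planning rates of 60% (qw) and 30% (placebo), 42 per group, 126 in total, about 150 randomized: SAP 1.4 and Protocol 10.1.
- Who is in each column: SAP 5.2.3, 5.4.1 and 2.4.1.1. Handling of discontinuation and missing data: SAP 5.2.2 and 5.4.2.
- d, the proportion of a bermekimab arm that stops before Week 16: not stated, so assumed over a range.
- r, the response among those still treated: assumed 60%, borrowed from the planning rate.

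**The plan's own figure.** With pooled variance and no continuity correction, n per arm = {1.96√[2 × 0.45 × 0.55] + 0.842√[0.60 × 0.40 + 0.30 × 0.70]}² / 0.30² ≈ 42, so 126 in three arms, and power at 42 per arm is 80.0%. This agrees with SAP 1.4. The step from 126 to 150 corresponds to 1 − 126/150 = 16%. That margin also serves safety data, so it is an upper reading of the dropout allowance and not a forecast of stopping before Week 16. The documents give no figure for the Week 16 to 36 display itself.

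**Denominator effect.** Suppose the drug effect is identical in every column and dropout is unrelated to response.
- qw or q2w column: r(1 − d)
- Crossover column: r
- Gap: r − r(1 − d) = r × d

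Example at d = 16% with 50 randomized per arm: 8 stop and 42 remain, of whom 0.60 × 42 = 25.2 respond. The qw column shows 25.2/50 = 50.4%. The crossover column shows 25.2/42 = 60%.

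| d before Week 16 | qw or q2w shows | Crossover shows | Gap (points) |
|---|---|---|---|
| 0% | 60.0% | 60% | 0 |
| 5% | 57.0% | 60% | 3.0 |
| 10% | 54.0% | 60% | 6.0 |
| 16% | 50.4% | 60% | 9.6 |
| 20% | 48.0% | 60% | 12.0 |

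**Sensitivity to the meaning of 60%.** SAP 1.4 gives 60% as an intent-to-treat rate. If it already counts dropouts as failures, qw shows 60% and crossover shows 0.60/(1 − d): 63.2%, 66.7%, 71.4% and 75.0% at 5%, 10%, 16% and 20%. The gaps are then 3.2, 6.7, 11.4 and 15.0 points.

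**Simulation** (50 per arm, 200,000 runs, r = 60%). At d = 16% the mean gap was 9.6 points, and the crossover column looked better in 82% of trials. With all columns restricted to those dosed at Week 16, that fell to 49%. Under a common rule, either that restriction or everyone kept with dropouts as failures, the mean gap was 0.1 points or less at every rate tried.

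**Continuous endpoints.** Zero improvement for early discontinuers shrinks the mean change by about the factor (1 − d) in the qw and q2w columns only.

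Stopping after Week 16 counts as failure in every column, so only stopping before Week 16 creates the imbalance.

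**The case against.** Much of the opposing case stands.

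- **Dose.** A reader might infer that the display distorts the dose conclusion. It does not: qw and q2w share one population rule and one discontinuation rule, so their randomized contrast carries no denominator artefact.
- **Loading regimen.** A reader might also infer that conclusions about loading are at risk. No objective or endpoint in the protocol or SAP assigns that question to these data. The planning use named in the SAP attaches to the Week 16 lock.
- **Direction.** It is tempting to say the crossover column will look better. By Week 32 those patients have had 16 fewer weeks of active drug, so only the denominator component has a known sign.
- **No formal test.** SAP 5.4.1.2 lists differences in least-squares means only through Week 16, and group means with intervals after that. Week 32 HiSCR is summarized by group.
- **Partial cover.** SAP 5.4.3.2.2 and 5.4.3.5.3.2 plan over-time supplementary analyses of AN count and HSSD 24-hour pain in which data after discontinuation are set to missing, with no stated Week 16 limit. In a Week 16 to 36 model this comes close to aligning the groups. The HiSCR supplementary analyses stop at Week 16.
- **Reasonable in itself.** Patients never given bermekimab cannot show a crossover response, and the restriction is openly stated.

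What remains is that the restricted column sits beside unrestricted ones under a sentence offering between-group assessment, and for HiSCR after Week 16 no planned analysis aligns them.

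**Conclusion.** The point holds for one comparison: crossover against continuous dosing after Week 16. The denominator component is r × d in favour of crossover. At an assumed 60% response among those still treated it is 3 to 12 points for an assumed 5% to 20% discontinuation before Week 16, and zero with none. These figures are illustrative. They assume the same drug effect in every column and dropout unrelated to response, and the documents state no dropout rate. The net displayed difference may have either sign.

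The Week 12 primary analysis, every comparison through Week 16 and the qw versus q2w contrast are untouched. This is a flaw in a descriptive display, worth correcting because the correction is cheap. It does not threaten the trial's main conclusions.

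**What to change.** 1. Add a Week 16 to 36 efficacy summary, including Week 32 HiSCR, that applies one condition (received study agent at Week 16) to all three groups. Show the denominator in each column and label it a non-randomized landmark set.
2. Keep the all-randomized display for qw and q2w, which remains the right one for comparing those two regimens.
3. Qualify the closing sentence of SAP 5.2.3 so that the mixed display is not used to compare crossover with qw or q2w. Do not delete it: it also covers the valid displays through Week 16 and the qw versus q2w comparison.

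The cost is SAP wording and one extra set of descriptive tables, with no new data. The downside is that the landmark set compares patients who remained on active drug with patients who remained on placebo. It removes the denominator artefact fully only if dropout is unrelated to response, so the label is needed.
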